What is the effect of a structured medication discontinuation clinical pathway designed to reduce polypharmacy on mean number of medications and patterns of discontinuation compared to usual practice?	Reduction in mean number of medications	Medication from reconciliation list	Mean number of medications	T ₀ , T ₆	t-test
			Proportion with successful reduction in medication number or dose	T ₆	Chi Square
			Composite variable of mean number of medication discontinuations or dose reductions	T ₆	t-test
What is the effect of a structured medication discontinuation clinical pathway designed to reduce polypharmacy on patient quality of life, frailty, cognition, mobility-related fatigue, nutritional status, physical function capacity, pain, sleep, patient enablement, medication self-efficacy, medication confusion, grip	Improved frailty, disease and treatment burden, quality of life, cognition, fatigue, nutritional status, physical function capacity and ability, pain, sleep, patient enablement, medication self-efficacy and	Frailty	Edmonton Frail Scale	T ₀ , T ₆	t-test
		Disease burden	Bayliss Disease Burden	T ₀ , T ₆	t-test
		Treatment burden	Brief Treatment Burden Scale	T ₀ , T ₆	t-test
		Quality of life	EQ5D-5L (economic analysis)	T ₀ , T ₆	t-test for all Chi squared for proportions
			SF36v2	T ₀ , T ₆	
		Cognition	Mini Mental State Exam	T ₀ , T ₆	

strength, falls and adverse events, and hospital admissions compared to usual practice?
	
lower/fewer falls, healthcare utilization, and adverse events will be reported in the intervention arm compared to the control arm at 6-months
	Fatigue	Avlund Mob-T and Limb-T scale	T ₀ , T ₆	
		Nutritional status	Mini Nutritional Assessment Short-Form	T ₀ , T ₆	
		Physical function capacity and ability	Mänty survey	T ₀ , T ₆	
			Timed up and go	T ₀ , T ₆	
			Global rating of change (balance)	T ₀ , T ₆	
			Grip strength	T ₀ , T ₆	
		Falls	Number	T ₀ , T ₆	
		Pain	Brief Pain Inventory	T ₀ , T ₆	
		Sleep	15-D (sleep item)	T ₀ , T ₆	
		Patient enablement	Patient Enablement Index	T ₀ , T ₆	
		Medication self-efficacy	Self-efficacy for appropriate medication use scale	T ₀ , T ₆	
		Healthcare utilization	Number of hospitalizations	T ₀ , T ₆	
			Number of ED visits	T ₀ , T ₆	
			Urgent care visits	T ₀ , T ₆	
			Proportion of patients with at least one hospitalizati	T ₀ , T ₆	

			on		
		Serious adverse events	Number	T ₀ , T ₆	
What is the cost-effectiveness of the structured medication discontinuation clinical pathway designed to reduce polypharmacy?	Not applicable	Cost per QALY	Data collection survey developed for study, EQ5D	T ₆	Cost Utility Analysis
What is the experience of patients as they go through a structured medication discontinuation clinical pathway designed to reduce polypharmacy?	Not applicable	Lived experience with deprescribing process	Semi-structured interview/patient diaries	T ₆	Descriptive analysis
What trajectories do patients follow in deprescribing?		Satisfaction with the intervention	5-point Likert scale developed for study	T ₆	t-test
Does deprescribing transform their bio/psycho/social experience of chronic disease and its management?		Satisfaction with care around medications	5-point Likert scale developed for study	T ₀ , T ₆	t-test
Are there social side effects of deprescribing?		Strength and weakness of intervention	Open-ended question	T ₆	Descriptive analysis
What are the experiences of the pharmacist and family physician of managing patients		Lived experience with deprescribing process	Semi-structured interview, field notes	T ₆	Thematic analysis

through the deprescribing process?		Confidence in medication discontinuation	5-point Likert scale developed for study	T ₀ , T ₆	t-test
		Five best/worst aspects of intervention	Open-ended question	T ₆	Descriptive analysis
		Implementation processes	NoMAD	T ₀ , after 3 of their patients have reached T ₃ and after all intervention group patients have completed T ₆ mark T ₃ , T ₆	Descriptive analysis

Table 2: Team contributions

Role	First name	Last Name	Contribution of hours per week (based on 35hr work week)	Role
Project Leader	[name]	7	Team lead; co-ordinate investigator and steering committee meetings; oversee the day-to-day operations; leading weekly meetings with the operational research team; supervise the research assistants in the day-to-day activites with weekly meetings including both sites; provide input into functional outcomes assessment and analysis; lead patient/family stakeholder engagement in design and KT aspects of study
Co-Investigator	[name]	1.75	Provide input into functional outcomes assessments
Co-Investigator	[name]	1.75	Provide input into functional outcomes assessments within LTC setting and engagement of family members as potential substitute decision makers

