1. Examine important feasibility measures and extent of implementation of the TAPER polypharmacy intervention in 2 LTC facilities
2. Examine signals of effectiveness of TAPER in LTC
3. Test measures for use in a larger randomised controlled trial
4. Collect data from family members to understand how to involve them in the deprescribing process, as well as their perspectives on the deprescribing process

3.4: Methodological Approach

- Describe how this project will be managed overall and who specifically will manage each major aspect of the study.
- Describe the overall study design, approaches, procedures and methods used in the study and why they are appropriate to meet the goals and objectives and deliver upon the proposed output(s).
- For example, if relevant, include aspects of participant recruitment, methods and tools used to assess participants for frailty, data collection, statistical analysis, etc.

Note: Study protocols must include frailty assessment of all study participants using a published frailty assessment instrument appropriate for the care setting.

Methods

Design

This is a feasibility RCT (1:1 patient randomization to either receive TAPER or usual care). The control group will be offered TAPER after 6-month outcomes are collected. In our experience using a randomized design in a full feasibility study is essential to ensure subsequent effective implementation in a large multi-site pragmatic RCT. This approach enables use of data in subsequent meta-analysis. Detailed testing of the proposed quantitative measures in this population is essential as score distributions may be clustered due to population characteristic similarities. In order to understand how to incorporate family and patient perspectives in priority setting, our experience with developing the approach for integrating patient priorities for TAPER in community-dwelling older adults indicates formal qualitative methods are best in developing the approach and producing publishable information for use by others working in the area.

We will randomize 90 patients (allowing for 10 dropouts). Participants will be 70 years or older and on > 5 medications. Based on our feasibility RCT in community-dwelling adults, this will provide adequate numbers to test feasibility of processes and provide information on outcome measure performance, recruitment rates and sample size calculation for a larger trial.

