Patients lists (aged 70 or older and on 5 or more medications) residing at each of the LTC facility will be generated by administrative staff. The study team will work with the LTC facility to develop a consent process. This process will include verbally reviewing expectations of participation, written consent, and confirming inclusion criteria. For those who are unable to provide written consent, consent will be sought by the substitute decision maker. We will provide information evenings for families of all residents considering participation.

Intervention

The intervention as a structured medication review through integrated consultations with a pharmacist and then a physician. The review is based on patient (or family where appropriate) preferences and priorities for treatment and available evidence. A 'pause and monitor' plan for medications suitable for discontinuation or dose reduction is developed, including agreed criteria for monitoring and for restarting medications (**see Figure 1 for TAPER diagram**). Key aspects of the intervention include:

1. **Resources, evidence and guidance to support medication discontinuation.** A systematic review of potentially useful tools has been completed and an eHealth platform (TAPERMD) developed for automatic detection of ADEs and screening for potentially inappropriate medications. It combines the Beers List, STOPP criteria, Anticholinergic Burden, hypotension burden, serotonin burden, QT burden and an interaction checker as well as deprescribing guidelines and evidence for benefits in older adults.
2. **Formal incorporation of patient priorities** to empower patients and clinicians to make choices driven by patient's personal values. A systematic literature review looking for existing tools and approaches and work completed with patient focus groups has informed this [21]. This study will seek family members input into how best to involve them in this process of priority setting.

3. **Collaboration.** The pathway supports collaborative review by pharmacists and physician.
4. **Integration of 'pause and monitor'.** Patient priorities, potential medication side effects, eTools, clinical consultation record and pause and monitor template plan are integrated in a web-based clinical pathway. This has been piloted with clinicians using a small number of patients in the LTC facilities.

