15. *Perceived change in side-effects and medication related symptoms* will be self-reported at 1-week, 3-month, and 6-month follow-up.

Semi-structured interview (Research Question 6)

Patients and family members will be asked to participate in a semi-structured interview to explore their experience with deprescribing, and their views on how to incorporate families' perspectives into deprescribing and strategies to address polypharmacy in LTC residents

Data Analysis

Means and standard deviations or proportions will be calculated for demographic information and study outcomes where appropriate. Analysis will involve t-tests or Chi-squared statistics where appropriate. Qualitative data will be analyzed by descriptive methods. See Table 1 for a full list of outcomes, timing of data collection and analysis.

Project Schedule

The project will be carried out over a 16 month period. All research, analysis and KT activities will be carried out in this time period. The project PI and the Research Associate will oversee all activities and will ensure the project schedule is followed (**See Figure 2 for the Project Schedule**)

Section 4 - Project Feasibility

4.1: Feasibility

- Identify all feasibility issues, barriers, challenges and limitations to the successful execution and completion of the study. Specifically address issue related to budget constraints, time constraints, structural issues, and organizational and personnel challenges that may delay or derail timely completion of the study.
- Describe how the investigative team plans on mitigating and overcoming these barriers, challenges and limitations.

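### No rule says how residents who cannot do the Timed Up and Go enter the comparison, and the t-test the plan implies does not adjust for the baseline time

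*Combined protocol and SAP*

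**What the plan says.** Section 3.5 (Study Measures) lists the Timed Up and Go and a timed 8-foot walk as performance measures, with main outcomes taken at baseline (T0) and 6 months (T6). Table 1 lists "Timed up and go" at both times with a blank analysis cell. The nearest entry above it, starting in the EQ5D-5L row, reads "t-test for all Chi squared for proportions". The only proportion in that block, "Proportion of patients with at least one" hospitalization, comes further down. The Data Analysis paragraph of Section 3.5 says: "Analysis will involve t-tests or Chi-squared statistics where appropriate".

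Eligibility is by age and medication count. Section 3.4 has "Participants will be 70 years or older and on > 5 medications", and its recruitment paragraph has "Patients lists (aged 70 or older and on 5 or more medications". The two differ on whether exactly five medications qualifies, but neither mentions walking or standing.

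The plan foresees some measurement difficulty. Section 3.4 warns that "score distributions may be clustered due to population characteristic similarities", and the feasibility measures in Section 3.5 include floor and ceiling effects, retention and refusal rates, and the team's view of how suitable data collection was. Section 3.4 also says the trial should "provide information on outcome measure performance, recruitment rates and sample size calculation for a larger trial".

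**The concern.** A time in seconds fits only the t-test among the methods named. A resident who cannot stand and walk, or cannot follow the instructions, produces no time. No visible section says how that resident is coded, counted or analysed, and there is no general missing-data rule. The situation is foreseeable: Section 3.1 describes mobility impairment as much more common in long-term care, Section 4.1 (Partnerships) expects some cognitive impairment, and Section 3.4 allows consent by a substitute decision maker.

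Two things are at stake. First, a resident who moves between able and unable during follow-up has undergone a real change in mobility, and a comparison of times alone leaves it out. Second, the larger trial needs to know how many residents cannot be tested, why, and whether that changes. A reason not recorded at the visit may not be recoverable. Separately, a t-test on T6 times ignores the T0 value the trial already collects, and a t-test on change subtracts it without adjusting for it.

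**Working it through.** **What can be reproduced.** Section 3.4 randomises 90 and allows for 10 dropouts: 90 − 10 = 80, or 40 per arm, which agrees with the 80 in the feasibility list. The documents state no alpha, power, effect size or SD, so there is no Timed Up and Go calculation to reproduce. Everything below is illustrative.

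**Same residents unable at both visits: loss of numbers.** With a share p unable, pairs of times = 80 × (1 − p). For p = 10/20/30% this gives 72/64/56. A larger trial analysed only in walkers would need 1/(1 − p) − 1 = 11/25/43% more residents. At two-sided 5% and 80% power the detectable difference is (1.96 + 0.84) × √(2/n): 0.63 SD at n = 40 per arm and 0.70 SD at n = 32 (20% unable). There is no bias if inability is unrelated to treatment.

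**Inability is the slow end of the scale and can change: loss of effect.** Assume a normal mobility scale (higher is slower), a true benefit of 0.5 SD, and 20% of controls unable, so the cut-off is c = 0.84. In the TAPER arm, 1 − Φ(0.84 + 0.5) = 9% are unable. The mean among those able is μ − φ(c − μ)/Φ(c − μ):
- control: 0 − 0.280/0.800 = −0.350
- TAPER: −0.5 − 0.162/0.910 = −0.678

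The difference is −0.328 SD, about 66% of the true 0.5.

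In seconds, assume log-normal times with median 25 s and log SD 0.5. The control mean is 25 × exp(0.125) = 28.3 s. The TAPER mean is 28.3 × exp(−0.25) = 22.1 s, a difference of about −6.3 s with nobody unable. By simulation, the difference among walkers at T6 is −4.0/−3.1/−2.4 s at 10/20/30% of controls unable. The ratio of times from ANCOVA on log seconds moves less, from 0.78 to 0.80/0.81/0.82.

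**Power (%).** Further assumptions: 40 per arm and T0–T6 correlation 0.7. There were 10,000 simulated trials per setting, but 3,000 for the log-change column, which was not run at 30%. A: inability can change. B: same residents unable at both visits.

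| Setting | T6 t-test, s | Change t-test, s | Change t-test, log s | T0-adjusted rank | T0-adjusted log ANCOVA |
|---|---|---|---|---|---|
| Nobody unable | 55 | 67 | 80 | 83 | 86 |
| A, 10% | 44 | 64 | 72 | 82 | 77 |
| A, 20% | 37 | 57 | 62 | 82 | 66 |
| A, 30% | 29 | 49 | – | 80 | 56 |
| B, 10% | 51 | 61 | 76 | 76 | 82 |
| B, 20% | 45 | 56 | 73 | 69 | 77 |
| B, 30% | 41 | 51 | – | 62 | 72 |

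At A, 10%, the rank test leads the T6 t-test by 82 − 44 = 38 points, but 83 − 55 = 28 of those are there with nobody unable. Most of that gain is baseline adjustment, not the handling of inability. With correlation 0.5 and 20% unable, the T6 t-test, change t-test in seconds, rank test and log ANCOVA have 36/35/68/45% in A and 46/40/52/61% in B.

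**What the trial could report.** If 18 of 90 (20%) were unable at T0, the 95% Wilson interval would be 13–29%.

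**The case against.** Table 1 does not plainly assign a t-test to this outcome. Its cell is blank and the layout is broken in the visible text, so a reader who infers an explicit instruction from the table goes too far. The Data Analysis paragraph is the firmer support, and even that leaves room for judgement. This objection limits the wording but does not supply a rule.

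The feasibility list already covers part of the ground. Floor and ceiling checks, retention and refusal rates, and the team's view of the data collection would show whether the test is usable here. That stands, but none of them says how untestable residents enter the comparison.

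Power is a weak yardstick for one of many secondary outcomes in a trial whose primary outcome is number of medications, and every input is assumed. That also stands. Function is not lost altogether: the Barthel Index, the Functional Ability Scale, the Mänty survey and a global rating of balance are planned.

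A reader might infer that both a rank analysis and log ANCOVA beat any t-test the plan could mean. The calculations do not support this. A t-test on change in log seconds is still a t-test; with correlation 0.7 and the same residents unable at both visits, it ties with the rank test at 10% (76% v 76%) and leads at 20% (73% v 69%). The rank test's clear lead depends on inability being the slow end of the scale, which nothing in the documents establishes.

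**Conclusion.** The gap is real and modest. As written, residents without a time drop out of the Timed Up and Go comparison, and the named tests make no adjustment for the T0 value. A benefit can be understated if inability differs or changes by arm; if the same residents are unable throughout, only power is lost. It would be too strong to say that the mobility result will be biased, because no document shows which pattern applies or how many residents are affected.

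The numbers above rest on an assumed share unable, SD, correlation and effect. In every setting computed, log ANCOVA had more power than the t-tests it was compared with, but much of that is ordinary baseline adjustment. The most durable gain is the record of who could not be tested and why, which serves the trial's aim of informing a larger one whatever the true share is. This is an improvement to consider on a secondary outcome; it does not affect the primary outcome or the sample size.

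**What to change.** 1. At T0 and T6, record one reason for each missing Timed Up and Go or 8-foot walk: unable (noting physical or cognitive), refused, absent or died. Report the proportion unable per arm with a 95% CI, and its change from T0 to T6.
2. Replace the t-test with T0-adjusted ANCOVA on log seconds among residents with a time at both visits, reported as a ratio of times with a 95% CI.
3. Beside it, as a supporting analysis, give a T0-adjusted rank comparison (Quade's rank ANCOVA) with unable ranked worst at both visits. In sensitivity analyses, vary whether cognitive inability and death are ranked worst or treated as missing.
4. Reconcile Section 3.5 with Table 1: the 8-foot walk, the Barthel Index and the Functional Ability Scale have no row in the visible table.

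The cost is some analysis wording, one code per missing test, which the physiotherapist planned in Section 4.1 could enter, and a short coding guide. There are downsides. Telling physical from cognitive inability is an assessor's judgement, and no visible section says the assessor is blinded. A rank result is less direct than seconds. Log ANCOVA still leaves out anyone unable at either visit, which is why items 1 and 3 should accompany it. If only one item is adopted, it should be item 1.
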